4.9 Triage Decision

One question is whether LLM assistance leads CHEWs to make better triage decisions. We will conduct two analyses to assess this.

First, for each (patient, note), we will construct an indicator for whether the CHEW triage decision (an intent to triage indicated in the SOAP note) and the MO suggested triage decision align. We will then regress this on whether the note is assisted, controlling for patient fixed effects.

Second, we will reconsider our primary outcomes excluding patients for whom the MO indicates that triage is recommended. This checks whether CHEWs specifically improve care for patients they should be treating directly.

5 Validation and Auxiliary Analysis

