4.2 Objective Misallocation of Treatment – Alternative Specifications

As auxiliary outcomes, we will run the same treatment misallocation regression as in Section 3.5 separately for each possible test (with only patient fixed effects).

In addition, we will assess the contribution of different types of non-compliance with test results by coding patient-test-note level indicators for

- Misallocation due to overprescription: a condition is treated that the patient is confirmed not to have
- Misallocation due to undertreatment: a condition the patient is confirmed to have is not treated
- Misallocation due to incorrect dosing or drug choice: a condition the patient has is treated but the dosing or medication chosen is inappropriate.

Note that the misallocation indicator in Section 3.5 is the union of all three of these cases. We will test each of these three as dependent variables in the same regression as the misallocation indicator.

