4.4 Medical Testing Decisions

We will assess the potential misallocation of medical testing in two ways. First, we will measure it based on the screening test outcome. For each test type, we will create an indicator that is coded as 1 if the CHEW recommends conducting a test that turns out to be negative, and a second indicator that is 1 if the CHEW neglects to request a test that turns out to be positive.

Second, we will also construct a (patient,test,note) level indicator that measures whether the CHEW and MO requested the same or a comparable medical test (e.g. the CHEW requested a malaria RDT whereas the MO requested a malaria bloodsmear).

Finally, we will combine these indicators and count as a mismatch if and only if either: i) a test was not requested by the CHEW but was positive, or ii) the test was requested by the cCHEW but the result was negative and no equivalent test was ordered by the MO. This accounts for the possibility that good clinicians might sometimes order tests which are more likely to be negative “just in case”.

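### The agreement indicator in SAP Section 4.9 scores missed and unnecessary triage alike, so its coefficient can be zero or positive while missed triage rises

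*SAP*

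**What the plan says.** Section 4.9 states its aim as "One question is whether LLM assistance leads CHEWs to make better triage decisions". For each patient and note it builds one binary variable, equal to 1 if the CHEW and the MO agree; the definition begins "we will construct an indicator for whether the CHEW triage decision (an intent to triage indicated in the SOAP note) and the MO suggested triage". The model follows: "We will then regress this on whether the note is assisted, controlling for patient fixed effects".

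A second analysis in the same section reads "we will reconsider our primary outcomes excluding patients for whom the MO indicates that triage is recommended". Its stated purpose is to look at patients whom CHEWs ought to manage themselves.

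For treatment and testing the SAP does separate the direction of error. Section 4.2 has one indicator for "Misallocation due to overprescription: a condition is treated that the patient is confirmed not to have" and another for "Misallocation due to undertreatment: a condition the patient is confirmed to have is not treated". The first part of Section 4.4 has an indicator for a requested test that is negative and "a second indicator that is 1 if the CHEW neglects to request a test that turns out to be positive". No section does this for triage.

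**The concern.** Better triage can mean fewer missed patients, fewer needless referrals, or both. Agreement with the MO treats one error of either kind as equal. A plausible effect of LLM feedback is to make CHEWs more cautious or less cautious overall. Such a shift moves the two error types in opposite directions, and the single indicator nets them. The result could then be reported as no effect on triage, or as an improvement, while the share of missed patients changed materially. The mirror case also holds: a real gain in sensitivity could be hidden by a rise in unnecessary triage.

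**Working it through.** **Inputs.** From the SAP: the agreement indicator and its patient fixed-effect regression (4.9), two CHEW notes per patient (2.2), and about 500 patients (2.1, a budget projection, used here only for illustration). The SAP gives no triage rate, effect size or power for this outcome, so there is no figure to reproduce. All rates below are assumptions.

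**Step 1: what the coefficient estimates.** With two notes per patient, a patient fixed effect and no optional controls, the coefficient b is the mean within-patient change in agreement, assisted minus unassisted. I read the MO's suggestion as one decision per patient, so it splits patients into two fixed groups. Let p be the share for whom the MO suggests triage. Sensitivity is the share of that group whom the CHEW note triages. Specificity is the share of the other group whom the CHEW note does not triage. Then

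b = p × Δsens + (1 − p) × Δspec.

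**Step 2: when it is zero.** b = 0 if Δspec = −Δsens × p/(1 − p). For a 30-point fall in sensitivity:

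| Assumed p | Fall in unneeded triage that cancels it |
|---|---|
| 5% | 0.30 × 0.05/0.95 = 1.6 points |
| 10% | 0.30 × 0.10/0.90 = 3.3 points |
| 20% | 0.30 × 0.20/0.80 = 7.5 points |

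Check at p = 10%, with sensitivity 80% to 50% and unneeded triage 10% to 6.7%: 0.10 × (−0.30) + 0.90 × (+0.0333) = 0. Missed triage has risen from 20% to 50% of the patients for whom the MO suggests it.

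**Step 3: a smaller fall, with and without an offset.** For a 20-point fall in sensitivity at N = 500:

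| Assumed p | More patients missed | Cancelling gain in specificity | b with no offset |
|---|---|---|---|
| 5% | 5 | 1.1 points | −1 point |
| 10% | 10 | 2.2 points | −2 points |
| 20% | 20 | 5.0 points | −4 points |
| 30% | 30 | 8.6 points | −6 points |

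**Step 4: wrong sign.** At p = 10%, a 20-point fall in sensitivity with a 5-point gain in specificity gives 0.10 × (−0.20) + 0.90 × 0.05 = +0.025. This would read as better triage.

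**Step 5: a constructed data set.** Take 500 patients, 50 with MO-suggested triage. Missed triage goes from 10/50 to 20/50, and unnecessary triage from 50/450 to 40/450.

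- Pooled: agreement is 440/500 in both notes, so b = 0.000 (robust SE 0.009, 95% CI −0.018 to 0.018).
- MO-triage patients: b = −0.200 (95% CI −0.312 to −0.088).
- Other patients: b = +0.022 (95% CI 0.009 to 0.036).

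The regression is the same in all three rows; only the split shows what happened.

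**The case against.** The strongest reply is that the consequences of missed triage are measured elsewhere. Section 3.2 tells the MO that treatment includes referrals, so a missed referral can count as a treatment error. Its expected harm then enters the DALY rating, and through that the severe-error outcome (3.3), the better-plan outcome (3.4) and the DALY comparison (4.6). Those ratings weight the two kinds of error by consequence. This stands, and a large rise in harmful missed referrals would probably leave a trace. But none of these outcomes identifies the error as one of triage, so they do not answer the question in 4.9.

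Four stronger readings are tempting, and the SAP does not support them.

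- A reader might infer that nothing looks at high-risk patients. Section 4.3 estimates the assistance effect on QALY loss by MO-rated severity, including severe illness. Severity is not the same as MO-recommended triage, but the gap is narrower than that inference.
- A reader might infer that triage is the only undirected measure. The match indicators in 4.1 and the CHEW–MO test comparison in 4.4 are also undirected.
- A reader might see the exclusion in the second analysis as a flaw. It is what that analysis's own question requires. For the first three primary outcomes, with one row per patient and note, the point estimate in the excluded group could even be recovered from the full and restricted results and their sample sizes, though not its interval. What is missing is a counterpart that reports on that group.
- A reader might infer that the two errors will cancel. Cancellation needs an offsetting fall in unnecessary triage of about the size in Step 2, and those rates were chosen to show that it can happen. Without an offset the pooled estimate does fall, only diluted.

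**Conclusion.** The point holds as a minor one. Section 4.9 asks about quality of triage but measures undirected agreement, and no analysis in the SAP identifies triage errors by direction or reports on the patients for whom the MO recommends triage. The formula for b follows from the SAP's own definitions. The sizes do not: they depend on the assumed p and rates. Over p from 5% to 20%, a 30-point loss of sensitivity would be hidden by a 1.6- to 7.5-point drop in unneeded triage. It remains minor because this is a secondary outcome, no primary result depends on it, and referral errors partly enter the MO's ratings. The last reason takes triage in 4.9 to mean referring the patient on, which the SAP implies but does not define.

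**What to change.** In Section 4.9, keep agreement as a summary and add:

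1. A missed-triage indicator (the MO recommends triage and the CHEW note does not) and an excess-triage indicator (the CHEW note triages and the MO does not recommend it), each in the same patient fixed-effect regression. Agreement equals 1 − missed − excess, so the agreement coefficient is minus the sum of the two new ones.
2. The same information on the scale of each group: the triage regression run separately in patients for whom the MO does and does not recommend triage. Up to sign and the factors p and 1 − p, these coefficients match those in item 1.
3. The 2×2 table of CHEW by MO decision, for the assisted and the unassisted note.

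The cost is a few lines of SAP text and two more regressions. Both decisions are already needed to build the agreement indicator, so no new data are required. The drawback is precision. The MO-triage group may be small (50 of 500 at an assumed 10%), and smaller still once the observations before 2/25 are dropped from MO-generated outcomes under Section 5.4; the SAP does not say how many those are. The interval for missed triage will be wide and should be reported with the estimate.

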5.1 Blinding

We will conduct checks to control for the possibility that imperfect blinding to the intervention (i.e. MO knowledge whether a patient note was “LLM assisted” or not) is impacting our results.

- We measure each MO’s beliefs about whether a given patient note was LLM-assisted with a survey question. We will analyze whether MO beliefs about whether a note was LLM assisted are predicted by true LLM assistance status.
- As a robustness check, we will control for MO beliefs about LLM assistance and for any order effects (i.e. identity of note A vs. B) in the main analysis.
- Ex post, if we find that MOs can reliably predict whether a note was LLM assisted, we will seek to identify whether there are specific outcome-irrelevant features of notes which aid in this prediction, and may run additional robustness checks on a subset of patients where this feature was absent, so blinding is better maintained.

Bias in the difference in evaluation between notes A and B can arise if the MO (i) correctly guesses which note is assisted by the LLM, and (ii) systematically rates notes more highly if they are assisted by the LLM, but *not* due to higher quality of care/true lower harm to the patient.

For the first note that each MO sees (note A), we elicit a “raw” evaluation score prior to seeing note B. This score is then amended into an “adjusted” final evaluation (the reason for the update is the potential for learning about note A, given the cognitively demanding task of the MO: for example, only when shown the highlighted differences between the two notes may the MO detect an error in note A.) In an ideal world, the “adjusted” rating simply reflects the MO’s evaluation given full information. This is the measure we use in most of our analysis. However, the “raw” score provides an opportunity for another blinding check, under the assumption that blinding is more problematic for note B than note A.

If this is the case, a cleaner but noisier estimate of our main effect can be obtained by using an across-patient comparison of the “raw” scores of assisted and unassisted SOAP notes A. This regression will be identical to our baseline specification, but omitting the patient fixed effects.

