3.1 Estimation

The primary analysis estimates the effect of LLM assistance on the four outcomes above, all broad indicators for the overall quality of care provided. Every outcome is measured both for assisted and unassisted SOAP notes. We will estimate

$$Y_{it} = a_i + bT_k + cX_{ik} + \epsilon_{ik}$$

where i is the patient (or patient-test combo in 3.5) and $k = \{A, B\}$ is the SOAP note. Y_{ik} is the outcome, a_i is a patient (patient-test) fixed effect, T_k is an indicator for “assisted” and X_{ik} are optional controls for order effects and unblinding (see next section).

We will calculate robust standard errors. In addition, we will separately report p-values using the Benjamini Hochberg procedure for controlling false discovery rates at $p = 0.05$. This will lead to a conservative estimate of the power of our statistical tests. We will also separately report means, standard deviation, and number of observations of each variable for the assisted and unassisted notes.

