3.3 Severe Treatment Error

The distribution of treatment error harm ratings is expected to be heavily skewed, with a large proportion of zeros.

We define severe errors as any errors (as above) that generate a harm rating at or above the 95th percentile of harm on the unassisted scale (pooling child and adult scales).

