3.4 An indicator for the better treatment plan

Based on the DALY rating of SOAP Note A vs. B (counting instances with no errors as 0 DALY loss) we will define an indicator that is 1 if the SOAP Note has the better treatment plan (lower DALY loss). This indicator is 0 for both notes if the notes are judged to be the same according to this question, asked after the MO rated Note A:

Are there any *meaningful* differences in the treatment plans of SOAP Note A and B?

Only if the answer is “yes” or “unsure”, the review of SOAP Note B proceeds.

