4.6 Average and Distribution of DALY lost

We use our DALY measure of harm indirectly in several primary outcomes (probability of error and severe error, which note is the better note). As a secondary outcome, we will measure the effect of LLM assistance on average DALY (this is not our primary outcome because we are concerned about power being limited due to a few outliers).

Additionally, we will show the full distribution of DALY ratings for the assisted and unassisted notes.

4.7 3rd Party MD Review of CHEW notes and MO notes

We will reassess our primary outcomes using the MD DALY ratings and subjective harm measures (section 2.5).

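### Does the belief-adjusted check in SAP 5.1 need a stated rule for reading a smaller adjusted effect?

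*SAP*

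**What the plan says.** Section 3.1 fits a patient fixed-effects model in which the terms X_ik "are optional controls for order effects and unblinding". It points onward for their use and does not say when they enter. Section 5.1 gives the use: "As a robustness check, we will control for MO beliefs about LLM assistance and for any order effects".

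The same section counts as bias only a rating advantage that is not "due to higher quality of care/true lower harm to the patient". If MOs turn out to recognise assisted notes, "we will seek to identify whether there are specific outcome-irrelevant features of notes which aid in this prediction", and a subset analysis may follow. It also plans a comparison of raw Note A scores without the belief term, described in these words: "a cleaner but noisier estimate of our main effect can be obtained by using an across-patient comparison". Outside 5.1, section 4.7 repeats the primary outcomes with the MD panel's ratings, and section 3.5 defines a primary outcome from screening tests.

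**The concern.** The guess is made by the person who rates the plans, after reading them. If MOs tend to take the better plan for the assisted one, the guess is a consequence of the treatment effect, and conditioning on it removes part of that effect. A smaller adjusted coefficient could then mean either that MOs recognised better plans or that they favoured notes they believed to be assisted. The two coefficients alone cannot tell these apart, and the SAP does not say how to read the difference. At stake would be a real benefit discounted as unblinding bias. Section 3.1 adds to the worry, because it places the belief term, as optional, inside the primary equation.

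**Working it through.** **Inputs.** The SAP gives no effect size, tie rate, guess rate or answer options for the belief question, so there is no plan figure to reproduce. Everything below rests on assumed values.

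**Model.** With two notes per patient, the fixed-effects model equals a regression of the within-patient difference d (assisted minus unassisted) on a constant and the belief difference G. Under forced choice, G = +1 for a correct guess and −1 for a wrong one. Then

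adjusted b = E[d] − c·E[G], with c = Cov(d,G)/Var(G).

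**Step 1: guesses follow quality, ratings unbiased.** Let D be the share of pairs that differ on the outcome, b = E[d], p the chance that the better note is guessed as assisted, and q = 2p − 1. Ties are guessed at random. Then E[G] = qb, Cov(d,G) = q(D − b²) and Var(G) = 1 − q²b², so

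proportional loss = q²(D − b²)/(1 − q²b²).

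For outcome 3 with b = 0.20, D = 0.40, p = 0.80: 0.36 × 0.36/(1 − 0.0144) = 0.131, so 0.200 becomes 0.174.

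| D | p = 0.80: adjusted b (loss) | p = 0.95: adjusted b (loss) |
|---|---|---|
| 0.30 | 0.181 (10%) | 0.156 (22%) |
| 0.40 | 0.174 (13%) | 0.140 (30%) |
| 0.50 | 0.166 (17%) | 0.123 (39%) |
| 0.70 | 0.152 (24%) | 0.089 (55%) |

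At p = 0.50 the loss is zero. For any error (D = 0.20, |b| = 0.10) it is 7% and 16%. The SAP points towards many ties: section 3.3 expects harm ratings "heavily skewed, with a large proportion of zeros", and section 3.4 says "This indicator is 0 for both notes if the notes are judged to be the same according to this question". That favours the upper rows. Other answer formats give larger losses for outcome 3: 17–39% and 36–71% if each note is guessed separately, and 33–35% and 79–80% if tied pairs get no guess.

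**Step 2: the two readings can be indistinguishable.** At p = 0.80 and D = 0.40, 56% of guesses are correct, since (1 + 0.6 × 0.20)/2 = 0.56. The same joint distribution of d and G arises from a real effect of 0.200 without bias, or from 0.174 real plus 0.026 bias with a style-driven guess.

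**Step 3: add a style cue.** Take E[G|d] = 0.20 + 0.60d with b = 0.20 and D = 0.40. Then E[G] = 0.32, c = 0.6 × 0.36/(1 − 0.32²) = 0.241, and adjusted b = 0.20 − 0.241 × 0.32 = 0.123. A rating bias of k per unit of G adds 0.32k to the unadjusted estimate only. For k = 0, 0.2 and 0.4 the unadjusted value is 0.20, 0.26 and 0.33, and the adjusted value stays at 0.123.

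**Step 4: is survival reassuring?** Not without conditions.
- Suppose there is no real effect, bias is proportional to a graded suspicion S ~ N(μ,1), and only its sign is recorded as the guess. With Φ and φ taken at μ, the share of bias left after adjustment is 1 − [2φ/(4Φ(1 − Φ))]·(2Φ − 1)/μ. At 60% correct guesses (μ = 0.253) this is 1 − 0.805 × 0.790 = 0.36. At 93% (μ = 1.476) it is 1 − 1.031 × 0.583 = 0.40.
- Suppose MOs link assistance with worse plans: E[G|d] = 0.4 − 0.4d, b = 0.20, D = 0.40. Then E[G] = 0.32, c = −0.4 × 0.36/0.8976 = −0.160, and the adjusted estimate rises to 0.20 + 0.160 × 0.32 = 0.25.

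**Step 5: the primary estimate.** Without the belief term, the estimate of b is the mean of d, whatever drives the guesses. None of the losses above reach it.

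**The case for a change.** The best case for a change is that an interpretation rule is credible only if written before the adjusted coefficient is seen, and that it costs only wording. The loss can also be large. In simulations of 500 patients with unbiased ratings, where guesses followed both quality and other cues (63–65% correct), the coefficient shrank by 29–68%. In one setting (errors 50% vs 40%) the share of significant results fell from 0.97 to 0.29. Stronger cues could reverse the sign. The neighbouring checks are imperfect too. For any error at an assumed 0.50 vs 0.40, the raw Note A comparison has a standard error of sqrt(0.49/n) with n per group, so power is 42% at n = 150 and 62% at n = 250. The paired estimate has 98% to 99.9% with 300 to 500 pairs. For outcome 3 the raw comparison works only through the DALY rating, of which section 4.6 says: "we are concerned about power being limited due to a few outliers".

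The direction of the effect stands, and so does the conclusion that attenuation alone does not show bias. The need to amend does not. The SAP rests no decision on the adjusted coefficient. A rule that also declared survival reassuring would fail in both cases of Step 4. Ranking the other checks above this one would not be safe either: a note feature that predicts assistance may track uptake of the LLM's advice, so a subset chosen on it may also condition on something downstream of treatment.

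**Conclusion.** No change follows. Sections 3.1 and 5.1 read together leave belief out of the baseline model and use it in a robustness check, so the word optional in 3.1 is at most loose drafting. Section 5.1 already carries the distinction a reader needs, between better care and favourable rating, and offers other evidence on blinding. The missing sentence, that attenuation or predictable guesses do not by themselves prove rating bias, is one a competent analyst would write when reporting. Adding it would alter no estimate, test or primary conclusion.

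The size rests wholly on assumed inputs. The loss in the secondary check is 10–55% for outcome 3 under forced choice with quality as the only cue, and more with added cues. It is nil if guesses are unrelated to quality and ratings are unbiased. The effect on the primary estimate is nil in every case.

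### The raw Note A blinding check is presented as the main effect with more noise, but raw scores can also miss errors, so a gap between raw and main results cannot by itself be put down to unblinding

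*SAP*

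**What the plan says.** SAP 5.1 has the MO rate Note A before seeing Note B (the raw score) and then amend that rating (the adjusted score). The stated reason is learning: "only when shown the highlighted differences between the two notes may the MO detect an error in note A". Of the adjusted score it says "In an ideal world, the “adjusted” rating simply reflects the MO’s evaluation given full information", and "This is the measure we use in most of our analysis".

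The section then offers the raw score as a further blinding check, "under the assumption that blinding is more problematic for note B than note A". If that holds, it says, "a cleaner but noisier estimate of our main effect can be obtained by using an across-patient comparison of the “raw” scores" of assisted and unassisted Notes A. The model is specified in one line: "This regression will be identical to our baseline specification, but omitting the patient fixed effects".

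Nothing is assumed about whether raw and adjusted ratings detect errors equally well. No rule is given for reading a difference between the raw result and the main result.

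**The concern.** The two adjoining paragraphs do not fit together. The first says a raw score may lack errors that the adjusted score contains. The second treats the raw contrast as the same quantity as the main effect, less exposed to unblinding and merely less precise. A missed error is not extra noise: it turns a 1 into a 0 on the error indicator of SAP 3.2, and so changes the expected value of the contrast. The loss also falls where it matters. Highlighted differences point to errors present in one note and not the other, and those errors make up the treatment effect.

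The stake is interpretation. Unblinding is a serious threat to the MO-rated outcomes, and this check is one of the tools for judging it. If the raw effect comes out smaller or non-significant, the present wording gives the reader no reason to think of anything but unblinding or chance. The SAP's own learning mechanism can produce the same pattern with blinding intact.

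**Working it through.** **Inputs from the SAP.** About 500 patients (2.1); notes labelled A or B at random (2.2), taken here as 250 assisted and 250 unassisted Notes A; a binary error outcome (3.2). A two-sided 0.05 test is used for illustration. The number of patients left after the exclusion of MO-rated data from before 2/25 (5.4) is not stated, so 500 is only the planning figure.

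**Assumptions.** The SAP gives no error rates, effect size, power or detection rates, so there is no figure to reproduce. Let p10 be the share of patients with an error only in the unassisted note, p01 only in the assisted note, and p11 in both. Blinding is perfect and the adjusted rating finds every error. Effects are reductions in the error rate.

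**Formulas.**
- Main (adjusted) effect = p10 − p01.
- Raw effect with equal solo detection s = s(p10 + p11) − s(p01 + p11) = s(p10 − p01).
- Raw effect with detection su for unassisted-only errors and sa for assisted-only errors, common errors being found equally often in both note types = su·p10 − sa·p01.

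The raw effect therefore equals the main effect only if solo detection is complete or the missed errors cancel, that is, p10(1 − su) = p01(1 − sa).

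**Equal detection.** With p10 = 15%, p01 = 5%, p11 = 25%, the adjusted error rates are 40% and 30%, an effect of 10.0 points. At s = 0.7 the raw rates are 0.7 × 40% = 28% and 0.7 × 30% = 21%, an effect of 7.0 points. A simulation of 4,000 trials gave means of 10.0 (within-patient) and 7.0 (raw across-patient) points, with standard deviations 1.9 and 3.9. Raw effect in points, with across-patient power in brackets, for three sets of assumed rates:

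| s | 15 / 5 / 25% | 10 / 2 / 10% | 20 / 10 / 40% |
|---|---|---|---|
| 1.0 | 10.0 (65.0%) | 8.0 (68.5%) | 10.0 (61.4%) |
| 0.9 | 9.0 (58.2%) | 7.2 (63.1%) | 9.0 (52.1%) |
| 0.7 | 7.0 (44.4%) | 5.6 (51.0%) | 7.0 (36.2%) |
| 0.5 | 5.0 (31.2%) | 4.0 (37.7%) | 5.0 (23.9%) |

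Columns give p10 / p01 / p11. Within-patient power on adjusted ratings is 99.9%, 100.0% and 98.6% for the three sets. In the first set at s = 0.7, the 95% half-width of the raw estimate is 7.5 points around an expected 7.0, so an interval that includes zero is an ordinary result with no unblinding at all.

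**A larger assumed effect.** Take p10 = 20%, p01 = 5%, p11 = 30%, with 95% of common errors found on solo reading. At 70% detection of one-note errors, the raw rates are 28.5 + 14.0 = 42.5% and 28.5 + 3.5 = 32.0%. The expected effect is 10.5 points against 15, and power is about 69% against about 93% for adjusted scores in the same across-patient comparison. At 50% detection the rates are 38.5% and 31.0%, an effect of 7.5 points with power about 42%.

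**Unequal detection.** With 15% and 5%:
- su = 0.6, sa = 0.9: 9.0 − 4.5 = 4.5 points.
- su = 0.9, sa = 0.6: 13.5 − 3.0 = 10.5 points.
- su = 1.0, sa = 0.7: 15.0 − 3.5 = 11.5 points.

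With 20% and 5%, su = 0.95 and sa = 0.70 give 19.0 − 3.5 = 15.5 points against 15. The raw effect exceeds the main effect whenever p01(1 − sa) > p10(1 − su).

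**Null case.** If p10 = p01 and detection is equal, the raw effect is s × 0 = 0. If detection is unequal, it is (su − sa)·p10, which is not zero.

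**The case against.** The best defence is that the SAP claims little. It presents this as an additional check under a stated assumption, warns that it is noisier, and discloses the learning mechanism just before. It plans no test that the raw and main effects are equal, and no rule that a smaller raw effect means unblinding. Blinding is also examined through MO beliefs, belief and order controls, possible feature-free subsets and the independent physician panel, and primary outcome 4 rests on screening tests and guidelines. All of this stands, and it limits the weight of the point. It does not supply the missing assumption about detection, and none of those checks says how a raw-versus-main gap should be read.

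A reader might infer more than the document supports:
- *That the raw effect must shrink.* SAP 5.1 says only that the MO may detect an error later. Shrinkage follows when detection is incomplete and about equal, or worse for unassisted-only errors; the cases above show that it can reverse.
- *That the check answers a different question.* With equal detection the raw contrast keeps the sign and the null of the main effect. In the 10.5-point case, with a standard error of about 4.3 points, it lies about 2.4 standard errors from zero and so nearly always has the right sign.
- *That all MO-rated primary outcomes are affected.* Outcome 3 compares Note A with Note B (SAP 3.4) and cannot be formed from raw Note A scores alone.
- *That sorting revisions by whether a new error was recorded would isolate favouritism.* A biased MO can newly record errors, and honest learning can change a harm rating with no new error.

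**Conclusion.** The description of the check in SAP 5.1 is wrong as written, because the paragraph before it undermines the property claimed. The raw contrast is less exposed to unblinding if the SAP's assumption holds, but it estimates the main effect only if raw and adjusted ratings detect errors equally, or if the misses cancel between note types. Otherwise it will usually be attenuated, by the factor s under equal detection. The size depends wholly on detection and error rates that the SAP does not give: minor at s = 0.9, a loss of 3 points in 10 at s = 0.7, half the effect at s = 0.5. The figures apply to the binary error indicator; the SAP does not say whether that yes/no item is amended along with the harm rating, but the argument is the same for any rating that rests on errors found.

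This is an auxiliary check on outcomes that can be formed from Note A alone. No primary estimate is affected. What changes is what a gap may be taken to show: a smaller raw effect is not by itself evidence of unblinding, while a raw effect in the same direction remains support for the main result.

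**What to change.** In SAP 5.1:

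1. Replace the description of the raw contrast. Say that it is less exposed to unblinding; that it estimates the main effect only if errors are detected equally in raw and adjusted ratings; that it will usually be attenuated otherwise; and that a smaller raw effect is not by itself evidence of unblinding.
2. Run the same Note A regression without patient fixed effects on the adjusted scores of the same patients, and report it beside the raw one. This separates the change due to dropping the fixed effects from the change due to the raw-to-adjusted revision. The revision itself still mixes learning with any unblinding.
3. Report descriptively the share and direction of raw-to-adjusted revisions of Note A by true assistance status, and do not use them as a test that separates learning from favouritism.

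The cost is a change of wording, one extra regression and a descriptive table, all from ratings already elicited. The downside is that the raw check will be presented as weaker evidence than it is now.
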